6.5 CONCOMITANT THERAPY

Not Applicable

6.5.1 RESCUE MEDICINE

Not Applicable

7 STUDY INTERVENTION DISCONTINUATION AND PARTICIPANT DISCONTINUATION/WITHDRAWAL

7.1 DISCONTINUATION OF STUDY INTERVENTION

Not Applicable

7.2 PARTICIPANT DISCONTINUATION/WITHDRAWAL FROM THE STUDY

Participants are free to withdraw from participation in the study at any time upon request. All analyses will be carried out according the ITT principle. The ITT population will be all patients randomized, regardless of whether or not treatment wax administered. All patients will be analyzed in the group to which they were randomized.

An investigator may discontinue or withdraw a participant from the study for the following reasons:

- Significant study intervention non-compliance
- A medical condition or situation occurs such that continued participation in the study would not be in the best interest of the participant

The reason for participant discontinuation or withdrawal from the study will be recorded in REDCap.

7.3 LOST TO FOLLOW-UP

A participant will be considered lost to follow-up if he or she fails to return for the scheduled postoperative visits and is unable to be contacted by the site staff after 3 attempts.

8 STUDY ASSESSMENTS AND PROCEDURES

8.1 EFFICACY ASSESSMENTS

This clinical trial does not require any study specific screening tests or procedures. Preoperative screening done as part of the standard of care for an arthroplasty patient will be used to determine patient inclusion and exclusion. Additionally, there are no required lab testing or procedures required for this clinical trial.

Following discharge patients will be followed in the outpatient office according to the postoperative standard of care visit schedule. The 2011 KSS Objective and Functional Outcome Measurements will be collected at the 8 week visit, or the office visit closest to these time points. Patients will be contacted via phone approximately 56 days from the date of surgery to capture any device related adverse events or other relevant patient outcomes. These KSS outcomes measures and follow-up phone calls are standard of care for the department.

8.2 SAFETY AND OTHER ASSESSMENTS

8.3 ADVERSE EVENTS AND SERIOUS ADVERSE EVENTS

8.3.1 DEFINITION OF ADVERSE EVENTS (AE)

Adverse event means any untoward physical or psychological occurrence in a human subject participating in research. An AE can be any unfavorable or unintended event including abnormal laboratory finding, symptom or disease associated with the research or the use of a medical investigational test article.

Medical Device Reporting:

This clinical trial is evaluating a commercially available marketed product. This product is being used according to the manufacture's guidelines.

This study will adhere to the adverse event reporting regulations of the Centers for Devices and Radiological Health (CDRH), part of the Food and Drug Administration (FDA) regulations. In accordance with the Safe Medical Devices Act of 1990 (SMDA) (Public Law 102-629) (21 CFR 803.32 (c)) ambulatory surgery centers, hospitals, outpatient diagnostic centers and other user facilities are required to report all incidents in which a medical device or user error may have caused or contributed to the death, serious injury or serious illness of a patient.

Adverse Event Reporting Period

The study period during which adverse events must be reported is defined as the period from the application of the bone wax to the end of the study treatment follow-up.

8.3.2 DEFINITION OF SERIOUS ADVERSE EVENTS (SAE)

Device User Facility Reporting Requirements of Serious Adverse Events:

A "device user facility" is a hospital, ambulatory surgical facility, nursing home, outpatient diagnostic facility, or outpatient treatment facility, which is not a physician's office. All deaths and serious injuries to which the device has or may have caused or contributed will be reported to the IRB, FDA and the manufacturer. The user facility will also submit annual reports to the FDA by January 1 of each year as described in 21 CFR 803.33.

Form 3419 Annual User Facility Report

- Medical Device Reporting Annual User Facility Report - Form FDA3419

- Instructions for Completing the Medical Device Reporting Annual User Facility Report, Form FDA3419

8.3.3 Serious Injury or illness definition:

“Serious injury or illness” means those injuries that are life threatening, result in permanent body function impairment or permanent damage to a body structure, or necessitate immediate medical or surgical intervention to prevent permanent body function impairment or permanent damage to a body structure (21 CFR 803.3) (r).

A device may have "caused or contributed to" a patient's death or serious injury, if the death or serious injury was or may have been attributed to the device or the device may have been a factor in the death or serious injury because of:

- Device failure
- Malfunction
- Improper or inadequate device design
- Manufacture
- Labeling or
- User error

▪ 8.3.3 CLASSIFICATION OF AN ADVERSE EVENT

8.3.3.1 SEVERITY OF EVENT

All adverse events that do not meet any of the criteria for serious should be regarded as ***non-serious adverse events***. Any non-serious adverse event felt to be related to the study device will be captured in the source documents and case report form.

- **Mild** – Events require minimal or no treatment and do not interfere with the participant's daily activities.
- **Moderate** – Events result in a low level of inconvenience or concern with the therapeutic measures. Moderate events may cause some interference with functioning.
- **Severe** – Events interrupt a participant's usual daily activity and may require systemic drug therapy or other treatment. Severe events are usually potentially life-threatening or incapacitating. Of note, the term “severe” does not necessarily equate to “serious”.

8.3.3.2 RELATIONSHIP TO STUDY INTERVENTION

All adverse events (AEs) must have their relationship to study intervention (device) assessed by the clinician who examines and evaluates the participant based on temporal relationship and his/her clinical judgment. The degree of certainty about causality will be graded using the categories below. In a clinical trial, the study product must always be suspect.

- **Related** – The AE is known to occur with the study intervention, there is a reasonable possibility that the study intervention caused the AE, or there is a temporal relationship between the study intervention and event. Reasonable possibility means that there is evidence to suggest a causal relationship between the study intervention and the AE.
- **Not Related** – There is not a reasonable possibility that the administration of the study intervention caused the event, there is no temporal relationship between the study intervention and event onset, or an alternate etiology has been established.

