Endpoints:	
Endpoints-Primary:
 
• Efficacy: To calculate estimated perioperative blood loss on POD 1 using the Hb-balance formula• Safety: To assess the patients for any device adverse events related to the use of bone wax 
Endpoints-Secondary:
 
• To calculate the Knee Society Scores (KSS), both objective and subjective scores, done preoperatively and 8 weeks postoperatively• To measure the difference between the preoperative and POD1 Hemoglobin (Hgb) and Hematocrit(Hct) values in the two patient cohorts

Study Population:	100 female and male patients (50 subjects in each arm) scheduled for unilateral total knee arthroplasty by Drs. [name] or [name]
Phase:	NA
Description of Sites/Facilities Enrolling Participants:	Department of Orthopaedics, Syosset Hospital
Description of Study Intervention:	Bone wax is a well-known topical hemostatic agent comprised of a mixture of beeswax, paraffin, and isopropyl palmitate. This inexpensive agent works by sealing the bleeding site and tamponades bleeding from the exposed cancellous bone. ²
Study Duration:	The study timeline is 18 months
Participant Duration:	Patients will be in the study from the date of consent until their 8 week postoperative visit.

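### The Related and Not Related definitions in section 8.3.3.2 are not mutually exclusive, so the count of related device events depends on the assessor

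*Combined protocol and SAP*

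**What the plan says.** The primary safety endpoint in the synopsis (section 1.1), repeated in section 3, is: "To assess the patients for any device adverse events related to the use of bone wax". Whether an event counts towards it turns on section 8.3.3.2, where the examining clinician assesses relationship "based on temporal relationship and his/her clinical judgment" and grades it in one of two categories.

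- **Related** is met by any one of three limbs: "The AE is known to occur with the study intervention", or "there is a reasonable possibility that the study intervention caused the AE, or there is a temporal relationship between the study intervention and event".
- **Not Related** is also met by any one of three limbs: "There is not a reasonable possibility that the administration of the study intervention caused the event", or "there is no temporal relationship between the study intervention and event onset, or an alternate etiology has been established".

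The section adds that "In a clinical trial, the study product must always be suspect". It does not say what to do with an event that meets both definitions, and it does not define a temporal relationship.

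On capture, section 8.3.3.1 says: "Any non-serious adverse event felt to be related to the study device will be captured in the source documents and case report form". Section 8.3.4 instead wants every adverse event documented whatever its relationship. Section 8.3.5 keeps anticipated postoperative events out of the eCRF. Section 9.4.4 makes the safety analysis descriptive.

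**The concern.** A two-category causality scale works only if each event falls in exactly one category. Here both categories are built from alternatives joined by *or*, and the limbs of one are not the negation of the limbs of the other. Two clinicians who both follow the protocol can give the same event opposite labels.

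That label defines a primary endpoint. The setting also gives little protection. Section 6.4 tells the surgeon and operating room staff the arm, section 2.1 says the surgeons have used bone wax as their standard of care for four years, and no independent adjudication is described. Section 4.2 blinds the postoperative hospital staff, but surgeons who know the arm may be among those who assess events later. At stake is whether the reported number of related events would be the same in another assessor's hands.

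**Working it through.** The plan gives no figure on this point, so the check is of the logic.

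**Inputs, all from section 8.3.3.2.** Each is yes or no:

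- K: the event is known to occur with the device.
- R: there is a reasonable possibility that the device caused it.
- T: there is a temporal relationship.
- A: an alternate etiology has been established.

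**Rules as written**

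- Related = K or R or T.
- Not Related = (not R) or (not T) or A.

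Four yes/no conditions give 2 × 2 × 2 × 2 = 16 combinations.

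**When T is yes (8 combinations).** Related is always met, so K does not matter and each row stands for 2 combinations.

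| R | A | Related met | Not Related met | Combinations |
|---|---|---|---|---|
| yes | no | yes | no | 2 |
| yes | yes | yes | yes | 2 |
| no | no | yes | yes | 2 |
| no | yes | yes | yes | 2 |

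Six of the 8 meet both definitions.

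**When T is no (8 combinations).** Not Related is always met. Related is also met unless K and R are both no, which happens in 2 combinations. Again 6 of the 8 meet both.

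**Total:** 6 + 6 = 12 meet both, 2 meet Related only, 2 meet Not Related only, and none meets neither. Some combinations are clinically unlikely, so 12 of 16 describes the rule and not how often events will be ambiguous.

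**A concrete case.** Section 2.3.1 lists infection and thrombosis among the risks associated with bone wax, so K is yes for either. If another cause is established, A is yes. Related is met through K and Not Related through A, whatever R and T are. The conflict therefore does not depend on how broadly temporal relationship is read.

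**If an established alternate cause is taken to rule out a reasonable possibility** (A implies not R), the second table row drops out. With T yes, 4 of the remaining 6 combinations still meet both.

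**Would deleting the timing limb from Related be enough?** Related becomes K or R, which fails in 4 combinations (K and R both no), all of them Not Related. Not Related fails in 2 (R and T yes, A no). That leaves 16 − 4 − 2 = 10 meeting both, so the structure of Not Related must change as well.

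**With Related = R and Not Related = not R:** 8 Related, 8 Not Related, 0 both.

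**The case against.** The best defence is that the scale is applied by a clinician using judgment, under a stated presumption of suspicion, and that few events are expected. On the site history in section 2.3.3, 3 infections in 1140 procedures, 50 bone wax patients would yield about 50 × 3/1140 = 0.13 infections. With a descriptive analysis, little hangs on the wording. The point about size stands. The point about judgment does not remove the defect, because judgment is exercised through categories that allow both answers. The presumption of suspicion is not a rule for conflicts, and it pulls against the alternate-etiology limb.

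A reader might infer more than the text supports in three ways.

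- *Timing makes almost every event in a waxed knee Related.* Section 8.3.1 does open the reporting window at wax application, but timing only permits the label. In 6 of the 8 combinations with T yes, Not Related is equally available. Temporal relationship is undefined and could be read narrowly.
- *The count could run from nearly all events to nearly none.* Not Related requires that another cause has been established for the event. That surgery or immobility could plausibly cause such events is not enough.
- *Relatedness is the only filter on the safety data.* Section 8.3.5 removes anticipated postoperative events before relatedness is considered, and section 8.3.4 asks for all events regardless of it. These sections conflict with each other and with section 8.3.3.1, but they do not make relatedness the sole gatekeeper.

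**Conclusion.** The definitions in section 8.3.3.2 overlap as written, and no rule resolves the overlap. An event that is known to occur with bone wax, or that follows it in time, and that also has an established other cause, meets both. For such events the classification is undetermined; it does not default to Related. The number of related device events, which is the primary safety endpoint, therefore depends on who assesses them.

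The size is limited. The documents give no basis for estimating how many events would be affected, and few are expected. No significance level, power figure or efficacy result changes. The conclusion rests on reading *or* in its ordinary sense in both definitions; it does not need a broad reading of temporal relationship. Separately, section 8.3.5 states that no bone wax-related events will occur in controls, so the label could not carry a between-arm comparison even if it were well defined.

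**What to change.** Rewrite section 8.3.3.2 along these lines:

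- Related: there is a reasonable possibility that bone wax caused or contributed to the event.
- Not Related: every other event.
- Neither timing alone nor the existence of another cause alone decides the category.

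This matches the contribution standard for serious injuries in section 8.3.2 and the reasonable-possibility standard in section 8.4.1. Two additions are best left out. Requiring that no other cause be more likely would exclude events to which the device may have contributed, against section 8.3.2. A separate tie-break has nothing to act on once Not Related is the complement of Related.

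Reconcile sections 8.3.3.1, 8.3.4 and 8.3.5 so that one statement governs which events are captured.

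The cost is a few sentences of protocol text and a CRF instruction, with no extra visits or staff. The downside runs both ways: some events that could have been set aside because of another cause will now count as related, and some that could have been counted on timing alone will not. Clinical judgment remains, but it is applied to one question with one answer.

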8.3.3.3 EXPECTEDNESS

The Principal Investigator will be responsible for determining whether an adverse event (AE) is expected or unexpected. An AE will be considered unexpected if the nature, severity, or frequency of the event is not consistent with the risk information previously described for the study intervention.

8.3.4 TIME PERIOD AND FREQUENCY FOR EVENT ASSESSMENT AND FOLLOW-UP

The occurrence of an adverse event (AE) or serious adverse event (SAE) may come to the attention of study personnel during study visits and interviews of a study participant presenting for medical care.

All AEs including local and systemic reactions not meeting the criteria for SAEs will be captured on the appropriate case report form (CRF). Information to be collected includes event description, time of onset, clinician's assessment of severity, relationship to study product (assessed only by those with the training and authority to make a diagnosis), and time of resolution/stabilization of the event. All AEs occurring while on study must be documented appropriately regardless of relationship. All AEs will be followed to adequate resolution.

Changes in the severity of an AE will be documented to allow an assessment of the duration of the event at each level of severity to be performed. AEs characterized as intermittent require documentation of onset and duration of each episode.

At each study visit, the investigator will inquire about the occurrence of AE/SAEs since the last visit. Events will be followed for outcome information until resolution or stabilization.

8.3.5 ADVERSE EVENT REPORTING

This clinical trial consists of postoperative total knee arthroplasty patients. DRE's common and expected in this group of patients include postoperative pain, nausea, hypotension, anemia, and dehydration. Events anticipated and expected in the postoperative arthroplasty patient will not be considered an adverse event for collection in the eCRF. Additionally, there are no study interventions for the control group. This group will be following the standard of care treatment for a total knee arthroplasty patient. Therefore, no adverse events related to the application of bone wax will be occurring in this group.

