2.3 RISK/BENEFIT ASSESSMENT

2.3.1 KNOWN POTENTIAL RISKS

The surgical techniques used to promote hemostasis will be consistent for all patients, except for the use of bone wax applied to the exposed cancellous bone following insertion of the prosthesis. There is a potential that patients in the control arm could have increase bleeding. The following risks have been shown to be associated with the use of bone wax: failed bone healing, foreign body reaction, granuloma growth, thrombosis, infection, and nerve compression

There is a small risk of an unintended breach of confidentiality, as there is in any research study that collects subjects' health information.

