3 OBJECTIVES AND ENDPOINTS

OBJECTIVES	ENDPOINTS	JUSTIFICATION FOR ENDPOINTS

Primary
 
• Efficacy: To assess whether bone wax results in superior hemostasis in patients undergoing primary unilateral TKA• Safety: To compare the safety profile between the 2 cohorts	
• To calculate estimated perioperative blood loss on POD 1 using the Hb-balance Formula• To assess the patients for any device adverse events related to the use of bone wax	
Use of the Hb-balance Formula provides a more accurate assessment of blood loss
 
To ensure there are no safety issues between the two cohorts

Secondary	
• To assess whether objective and functional outcomes in patients undergoing primary unilateral TKA differ between the two patient cohorts• To determine if there is a difference in blood loss between the two cohorts 
• To calculate the Knee Society Scores, both objective and subjective scores, done preoperatively and 8 weeks postoperatively• To measure the difference between the preoperative and POD1 Hemoglobin (Hgb) and Hematocrit (Hct) values in the two patient cohorts	
The Knee Society Score is a validated tool to assess both objective and subjective outcomes. The collection of the KSS is a standard of care for Drs. [name] and [name]'s TKA patients.
 
These values will be used to assess hemostasis over time

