5.2 EXCLUSION CRITERIA

1. Patients unable to take aspirin or apixaban for VTE prophylaxis
2. Allergy to any of the ingredients in bone wax (beeswax, paraffin, or isopropyl palmitate)
3. Patients taking clopidogrel (Plavix), ticagrelor (Brilinta), or prasugrel (Effient) or any other antiplatelet medication (except for aspirin 81 mg)
4. Patients unable to get IV TXA for any reason
5. Patients requiring anticoagulant treatment prior to surgery
6. Any medical condition that in the opinion of the investigator would require special fluid management protocols during or after surgery
7. Allergy to TXA

8. Blood transfusion within 1 month of surgery
9. Patients who are unwilling to undergo blood transfusion, if necessary
10. Patients who have habitual opioid use
11. Patients who have a psychiatric or mental illness which could impair the consent process or ability to complete patient-reported questionnaires
12. Fixed motor deficit affecting functional assessment of the knee
13. Patients with a contraindication to spinal anesthesia
14. Patients receiving erythropoietin therapy for anemia
15. Patients who are unable to stop their daily aspirin, aspirin-like products, and/or non-steroidal anti-inflammatory agents 7 days prior to surgery for any reason
16. Patients with a contraindication for the pneumatic tourniquet applied in the operating room

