8.3.8 EVENTS OF SPECIAL INTEREST

Not Applicable

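### Section 8.3.5 keeps expected postoperative events out of the eCRF through an open list, conflicts with 8.3.3.1 and 8.3.4, and does not protect the known bone wax harms of 2.3.1

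*Combined protocol and SAP*

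**What the plan says.** Section 3 sets a primary safety objective, "To compare the safety profile between the 2 cohorts", and pairs it with this endpoint: "To assess the patients for any device adverse events related to the use of bone wax". Section 2.3.1 lists six risks associated with bone wax: "failed bone healing, foreign body reaction, granuloma growth, thrombosis, infection, and nerve compression".

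Section 8.3.5 first gives examples of ordinary postoperative events: "DRE's common and expected in this group of patients include postoperative pain, nausea, hypotension, anemia, and dehydration". It then sets the collection rule: "Events anticipated and expected in the postoperative arthroplasty patient will not be considered an adverse event for collection in the eCRF".

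Four other sections bear on the same events:

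- Section 8.3.3.1 sends any non-serious event thought to be device-related to the source documents and the case report form, with no exception for expected events.
- Section 8.3.4 captures all non-serious adverse events on the case report form and requires documentation whatever their relationship to the device.
- Section 8.3.3.2 requires relatedness to be graded for all adverse events.
- The section on special-interest events is empty: "8.3.8 EVENTS OF SPECIAL INTEREST Not Applicable".

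Section 9.4.4 plans a descriptive safety analysis only.

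**The concern.** Expectedness usually decides how fast and to whom an event is reported. In 8.3.5 it decides whether an event enters the eCRF as an adverse event. The word introducing the examples leaves the set open, so whoever applies the rule must decide what else belongs in it. Nothing says that the harms already attributed to the device stay outside it.

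Infection and thrombosis are the two harms in 2.3.1 most open to being called anticipated after any knee replacement. Section 2.3.3 says surgical site infections are tracked as a quality metric. Section 5.2 assumes thromboembolism prophylaxis for everyone, since it excludes "Patients unable to take aspirin or apixaban for VTE prophylaxis". If such an event were left out as expected, a finding of no safety problem could partly reflect the collection rule rather than the patients. The between-arm comparison promised in section 3 also needs these events recorded in the same way in controls.

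**Working it through.** The plan gives no figure on this point to reproduce. The main check sets the sections side by side; the arithmetic then shows the scale.

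**1. One event under each rule.** Take a superficial wound infection in a wax-arm patient.

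- *If 8.3.3.1 and 8.3.4 prevail:* it is an untoward occurrence under 8.3.1, so it goes on the case report form. Relatedness is graded under 8.3.3.2, where a temporal relationship is enough for a grade of related. It can then count in the primary safety endpoint.
- *If 8.3.5 prevails:* it is judged anticipated after arthroplasty and is not an adverse event for the eCRF. Grading under 8.3.3.2 applies to adverse events, so it may never be graded. The endpoint is defined by relatedness, so the event does not enter it.

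No section ranks these rules. Because 8.3.5 removes the event from the adverse event category, staff could follow it and believe they had also complied with 8.3.3.1 and 8.3.4.

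**2. Other routes.** Section 8.3.2 covers deaths and serious injuries to which the device may have contributed. A superficial infection need not qualify, and those reports go to the IRB, the FDA and the manufacturer rather than to the study dataset. Section 8.3.6 concerns unanticipated device effects, which 8.4.1 defines as not previously identified in nature, severity or degree of incidence. A known harm can fall outside that route too.

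**3. Scale.** Inputs: 50 patients per arm (section 9.2); 2 superficial and 1 deep infection in 1140 bone wax procedures (section 2.3.3).

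Exact (Clopper-Pearson) 95% limits for the wax arm:

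- 0/50: upper limit 1 − 0.025^(1/50) = 7.1%, so 0 to 7.1%.
- 1/50 = 2.0%: lower limit 1 − 0.975^(1/50) = 0.05%; upper limit, the 0.975 quantile of Beta(2, 49), = 10.6%.

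Infections expected at the site's own rate:

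- Rate: (2 + 1)/1140 = 0.26% (exact 95% CI 0.05 to 0.77%).
- Expected in 50 patients: 50 × 3/1140 = 0.13.
- Chance of at least one: 1 − (1 − 3/1140)^50 = 12.3%.

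The documents give no thrombosis rate. The table shows assumed rates for any one harm:

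| Assumed rate | Expected in 50 | Chance of at least one |
|---|---|---|
| 1% | 0.5 | 39% |
| 2% | 1.0 | 64% |
| 5% | 2.5 | 92% |

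Counts will therefore probably be very small, and one omitted event changes what is observed.

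**The case against.** The strongest reply is that 8.3.5 concerns routine postoperative complaints. Its five examples are everyday events, and an infection rate of 0.26% sits poorly with a category described as common. Neither infection nor thrombosis is named. Tracking infections as a quality metric shows that they are watched, and requiring that patients can take prophylaxis does not classify thrombosis as an event to be ignored. Sections 8.3.2, 8.3.3.1 and 8.3.4 still require capture or reporting. Section 8.3.3.2 says the product must always be suspected. The schedule of activities assesses device adverse events from the day of surgery to the follow-up call, and section 10.1.9.1 enters related events in REDCap.

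Most of this stands, and it rules out three stronger readings that a reader might infer:

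- *That all six harms are expected, and so exempt, because 2.3.1 lists them.* Section 8.3.3.3 says "An AE will be considered unexpected if the nature, severity, or frequency of the event is not consistent with the risk information previously described", but it judges against the risk information for bone wax and does not govern collection. Section 8.3.5 asks what is expected after arthroplasty. Being a known wax harm is not its test, and foreign body reaction or granuloma growth would fit it poorly.
- *That known harms are not collected at all.* The exclusion is from the eCRF, and the sections above point the other way.
- *That one missed infection would decide the safety result, or that one recorded infection would be a signal.* The analysis is descriptive, the two intervals overlap heavily, and the 0.26% rate itself comes from wax-treated knees.

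What the reply does not remove is the conflict. The list is open, no order of precedence is given, and an event taken out of the adverse event category may never reach the step where relatedness would bring it back. The surgeon knows the allocation (section 6.4), and nothing requires the exemption to be applied blind.

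**Conclusion.** The point holds as an unreconciled conflict with an open-ended exemption. Section 8.3.5 leaves the excluded set undefined, contradicts 8.3.3.1 and 8.3.4, and gives no protection to the harms of 2.3.1. The loss of an infection or thrombosis from the primary safety endpoint is a risk the wording permits, not a stated rule, and it is less plausible for foreign body reaction or granuloma growth.

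The size is one event at a time: an observed 2.0% or 0% in 50 wax patients, with upper 95% limits of 10.6% or 7.1%. Neither result would establish or exclude harm. This conclusion assumes that staff could read 8.3.5 as overriding the other two sections, which the text neither confirms nor forbids. The infection figures assume that the site's past rate carries over to the trial.

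**What to change.** 1. In 8.3.5, limit the exemption to a closed list of the five events now named, and state that it does not apply when such an event is judged device-related. Add that no other event is left out of the eCRF because it is expected.
2. State in 8.3.5 how it fits with 8.3.3.1 and 8.3.4, so that the three sections give one rule.
3. In 8.3.8, replace the present entry with the six harms of 2.3.1. Record them in the eCRF for every patient in both arms, whatever their expectedness or judged relatedness, and tabulate them by arm under 9.4.4. This supports the between-cohort comparison in section 3.
4. As a consequence, give controls a start point for event collection, because 8.3.1 starts the period at wax application.

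The cost is protocol wording, a short checklist at contacts already in the schedule, and a few more events to enter. The sample size and the efficacy analysis do not change.
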